#### 8. STUDY PROCEDURES

#### 8.1 Recruitment and Consent

Subjects will be recruited using targeted mailings and direct contact. Similar to our pilot study, we will recruit in-person consecutive BCS who are being seen for care at the Indiana University Health Systems clinics including the IU clinics on campus (IUSCC) (including Eskenazi Hospital) and the associated Northside clinic in Carmel, IN.

We will also recruit through mailings. Similar to our pilot, we will use: (1) the IU Cancer Center tumor registry's 4,111 potentially eligible BCS, who fit our revised eligibility criteria and the (2) the Indiana Clinical and Translational Sciences Institute patient registry which has over 1,975 potentially eligible BCS. We will review lists to ensure that no duplicate inquires will be sent to potentially eligible BCS.

For in clinic recruitment, [name] (co-I) or designee will get permission from patients to allow project staff to enter the patient's room during a clinic visit to introduce the study.

#### Introduce study and screen for eligibility/interest

For in clinic recruitment, the project recruiter then sequentially approaches each woman at the end of her clinic visit with the physician and describes the purpose and nature of the study.

For those that contact our office in response to a mailing, study staff will discuss the study requirements and screen for eligibility (phone or in person. Those determined to be ineligible due to depressive symptoms will be referred to their attending physician for follow-up.

**Distribute study information:** Following screening, study staff will send or hand out a study packet. Packets will contain a cover letter with contact information; a study brochure; copies of the informed consent statement and HIPAA-mandated authorization to allow use of protected health information; and a stamped, addressed envelope for returning the signed consent and authorization forms.

**Obtain informed consent:** Women who are eligible and interested will be consented in person in the clinic. Those women who do not return a signed consent will receive a phone call one week following their screening date to verify interest in participating and provide additional information if needed. Interested women will be instructed on the consent process. Informed consent will follow the requirements of the university's institutional review board

**Eligibility/Baseline Assessment:** After the signed written consent and HIPAA authorization forms are received, research staff will telephone the participant and arrange a mutually convenient appointment. Assessments will be completed in a private room at the university. First, eligibility will be confirmed via self-report by the participant.

If ineligible, the subject will be thanked for her time and interest in participating.

If eligibility is confirmed, the appointment will continue, and the other baseline assessment measures will be administered. Once the neuropsychological assessment and questionnaires are completed, the tester will review them and obtain data from the participant on any missing items

**Randomization:** Building on our pilot studies, BCS will be randomly assigned to one of two groups: BrainHQ cognitive training or attention control. Assignments will be in a random order generated by a computer using blocks of 8, to ensure filling of treatment groups. Randomization will occur as close to the start of the training sessions as possible to minimize study drop-out.

Neuropsychological testing, completion of questionnaires and collection of a blood sample for BDNF will be collected at two time points during the study. Baseline (T1) data will be collected prior to the initiation of the intervention or attention control computerized training. Follow up assessments and BDNF blood sample will be collected post-intervention within 90 days of completing the intervention or attention control computerized training (T2)

Serum for BDNF analysis and all biomarkers that are part of this study will be prepared by laboratory services at IU and will be securely and confidentially (blood sample code) stored in the Analyte Laboratory within the Translation Core of the Center for Diabetes and Metabolic Disease under management of [name] (Co-I). The BDNF serum levels will be batch analyzed following collection of all samples following the manufacturers' ELISA protocol. The ELISA assay has standards ranging from 7.8 to 500 pg/ml BDNF (this is the possible range for all samples).

The study will also examine biomarkers that can affect brain functioning including neurotropic factor, proinflammatory cytokines, cortisol, and dehydroepiandrosterone (neuro steroid) DHEA.

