## 5. STUDY DESIGN

The proposed design is a two-group, randomized, controlled trial. After providing consent and completing a baseline assessment, a total of 68 eligible BCS will be randomized to computerized cognitive training or computerized attention control. Training sessions have been standardized across the BrainHQ training and attention control groups with each group completing up to 40 hours over 10 week period (total of up to 40 hours), with the dose based on previous research. Outcomes will be assessed at baseline and immediately post-intervention (within 90 days).

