Novelty	Individualized feedback and rewards built in to respond to the participant, game features to improve satisfaction	Feedback and rewards not provided, may incur some satisfaction on their own	complete of co interventi attention			

Based on the randomization, the project manager will provide verbal and written instruction for

accessing and using the program and the minimum amount of practice required. BrainHQ and computerized attention control programs will capture the date and time the participants participate in the study.

ntervention: Α assessment will icted immediately tervention (T2). n our pilot study, post-intervention ent and BDNF draw will be d within 90 days ompleting the on (T2) training or control sessions.

edures for

Monitoring Treatment Fidelity: As in our pilot, procedures for monitoring treatment fidelity will

be guided by the Treatment Fidelity Checklist. Both groups have been standardized in dose (length and content) and delivery method (in-home). Intervention dose will be carefully monitored using the computer software built within BrainHQ and Rescue Time software for the active attention control (total time on task). These variables will be examined and used in the analysis. The PI will be responsible for oversight of treatment fidelity The neuropsychological tester will be blinded to group status. The project manager will ensure the participants understand and are utilizing the program. Treatment dose and content will be carefully monitored through the InSight program.

**Qualitative assessment**: individual interviews will be conducted over the phone with members of the intervention group to understand the perceived facilitators and barriers to use of the intervention. All interviews will be conducted after the intervention, voice recorded digitally and labeled with a patient identification number.

Accrual & Retention: Several steps will be taken to ensure high rates of accrual, retention, and representation of minority BCS. These include (1) using culturally appropriate printed study information; (2) contacting potential subjects in person in the clinic, which has been shown to be preferred over unsolicited telephone calls  and to be more effective in recruiting minority subjects; and (3) providing participant incentives of \$20.00 for every assessment completed (\$40.00 for both) to offset subject burden.

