ANCOVA, to compare the effects of cognitive training to attention control will be used. The dependent variables, cognitive performance measured post-intervention, will be the primary outcomes. The baseline cognitive performance will be adjusted for as a covariate. The other independent variables will be the fixed effect for training group (BrainHQ, attention control), the Time effect, and the interaction term of Time-by-Training Group. The primary test of interest will the Group effect, which compares the two randomized groups on the outcome. The second most important test will be the interaction test to determine whether change over time differs for the two groups. We will also assess the Time effect, which tests whether scores generally changed in one direction for both groups combined. In addition, to ensure equivalence across groups potential covariates will be adjusted for in the models on which the various intervention and control groups significantly differ after random assignment at a liberal p-value of <.10. Effect sizes between the two groups will be computed as differences between adjusted means divided by pooled standard deviations. The significance level will be <.05 for all tests of hypotheses. Aim 5 provides the estimation of the effect of cognitive training on serum BDNF. Similar to Aims 1 and 2, a GLMM will be fitted to the data to estimate this effect, while controlling for potential known confounding effects including, age, education, smoking status, body mass index, medications, physical activity (per DUKE Activity Status Index) that may influence BDNF interpretation prior to hypothesis testing; although the RCT design will likely balance these factors.

**Power analysis:** We are adequately powered for estimating effect sizes or preliminary efficacy (Aim 2). Sample size is based on Aim 2 preliminary tests of post-intervention efficacy of the intervention on continuous outcomes. A difference between means equal to 0.80 standard deviations represents a large effect size, a medium effect size is 0.50, and a small effect size is 0.20.96 Using the Nquery software, a sample size of 30 in each group will provide 86% power for a two-sided t test to detect a large effect size of 0.80 when alpha is .05, to detect small or medium effect sizes.

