**Methods for Handling Missing Data and Dropouts:** The GLMM approach to analysis allows use of all available data, including from participants who have incomplete (i.e., partially missing) data. We will compare those who dropped out to those who completed the study on various demographic and treatment factors and on intervention group membership. To the extent that differences exist, we will describe this bias and its potential effects on the results of our analysis. Additionally, we will attempt to determine missing data patterns, and, if cell sizes permit, will incorporate this information into the analyses by re-running the GLMM with incorporation of the missing pattern as a nominal covariate.

Additionally, the influence of treatment dose (i.e.: sessions completed) will be evaluated to determine if it should be included as a covariate in the GLMM. Participants will be randomized only after completing baseline assessment. There are only two possible missing data patterns: baseline and immediate post only.

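### A single printed block size of 8, with no stated concealment of the list, would let a staff member who knows past assignments foresee about 19% of the 68 allocations

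*Combined protocol and SAP*

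**What the plan says.** The randomisation paragraph of section 8.1 says that "BCS will be randomly assigned to one of two groups: BrainHQ cognitive training or attention control", and then "Assignments will be in a random order generated by a computer using blocks of 8, to ensure filling of treatment groups". It gives no other block size, no stratification factor and no explicit allocation ratio. Section 5 sets the total: "a total of 68 eligible BCS will be randomized to computerized cognitive training or computerized attention control".

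On timing, section 8.1 says "Randomization will occur as close to the start of the training sessions as possible to minimize study drop-out", and section 10 adds "Participants will be randomized only after completing baseline assessment".

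On who learns the assignment, section 8.2 says "Based on the randomization, the project manager will provide verbal and written instruction for" use of the assigned program, and later "The project manager will ensure the participants understand and are utilizing the program". Section 8.2 names only the neuropsychological tester as blinded.

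The protocol does not say who generates or holds the list, how an assignment is released, or whether the block size is kept from staff. Section 7 describes OnCore as a system for registration and data capture, not for concealed allocation.

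**The concern.** With a known block size, an assignment becomes certain once either arm has used its four places in the block. The project manager deals with women in both arms according to their assignment, and so is in a position to know the sequence so far. Section 11 also gives this role the monitoring of data entry and reports on the whole dataset.

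If someone who can foresee the next arm also influences who is randomised next, the groups can come to differ in ways that randomisation is meant to prevent. A keen or computer-able woman might be steered towards BrainHQ, knowingly or not. The outcomes most exposed are self-reported cognitive function (Aim 2) and acceptability, satisfaction and adherence (Aim 1). Section 10 adjusts for the baseline score and for covariates that differ at p < .10. Section 9 lists no measure of motivation or computer skill, so that adjustment could not be relied on to remove such a difference.

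**Working it through.** The plan gives no figure for predictability. Its one design calculation is power: "a sample size of 30 in each group will provide 86% power for a two-sided t test" at an effect size of 0.80 and alpha .05. The noncentral t gives 86.1%, so the figure is reproduced. It is used here only because equal groups imply 1:1 allocation.

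**Inputs**
- Block size 8 and two arms (section 8.1).
- 1:1 within blocks, so 4 + 4 (assumed; implied by section 10).
- One list (assumed; no stratification is described).
- Total 68 = 8 × 8 + 4: eight full blocks and four assignments of a ninth (section 5).
- An observer who knows the block size and all earlier assignments (assumed; compatible with the project manager's tasks).

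**Certain assignments in a full block.** There are C(8,4) = 70 orderings. Assignment k is certain if one arm filled its four places among the first k − 1, which has probability 2 × C(k−1, 4)/70:
- 1st to 4th: 0
- 5th: 2 × 1/70 = 2.9%
- 6th: 2 × 5/70 = 14.3%
- 7th: 2 × 15/70 = 42.9%
- 8th: 2 × 35/70 = 100%

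The sum is (2 + 10 + 30 + 70)/70 = 112/70 = 1.6 per block. This agrees with the closed form 2m/(m + 1) = 8/5 for m = 4. As a share, 1.6/8 = 20%.

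**Over the planned 68.** None of the four assignments in the ninth block is certain, so the expected number is 8 × 1.6 + 0 = 12.8, and 12.8/68 = 18.8%.

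**Best guess.** The observer names the arm with more places left. With a and b places left, the guess is right with probability max(a, b)/(a + b). Averaged over the 70 orderings, this gives 5.329 correct of 8 (66.6%) in a full block. For the first four positions of a block it gives 1/2 + 4/7 + 4/7 + 22/35 = 2.271. Over 68: (8 × 5.329 + 2.271)/68 = 44.9/68 = 66.0%, against 50% without blocking.

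**Randomly varying block sizes.** This was simulated with 600 lists of 68 per row. The observer is assumed to know the set of sizes but not their order.

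| Block sizes | Certain | Best guess right |
|---|---|---|
| 8 only (check) | 18.8% | 65.9% |
| 4, 8 | 7.4% | 67.9% |
| 4, 6, 8 | 2.2% | 67.8% |
| 6, 8, 10 | 1.6% | 66.1% |

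Varying the sizes nearly removes certainty but does not reduce best-guess accuracy.

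**The case against.** The strongest objection is that selection bias needs one person who both foresees the next arm and decides who is randomised next, and the protocol does not place both in one role. Section 8.2 gives the project manager tasks after assignment. Section 8.1 gives recruitment, screening, consent and baseline to a recruiter, study or research staff and the tester. This stands, and it limits the point to an opportunity.

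A reader might infer from the timing sentence that staff choose among women waiting to be randomised. The text does not support that. It shortens the gap between assignment and training, section 8.2 has randomisation follow baseline, and training is individual and at home. The section 12 timeline shows enrolment from June to January, eight months, so 68/8 = 8.5 women a month, about two a week. At that rate few women would be waiting at once. Even so, no rule requires randomisation in order of baseline completion.

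There are also safeguards. Clinic patients are approached consecutively, baseline precedes randomisation, the tester is blinded, and time on task is recorded by software. These protect measurement and would make a difference in dose visible, but they do not conceal the next assignment.

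A fixed block of 8 is a recognised choice, and a known block of 8 is less predictable than one of 4 or 6 (20% certain, against 33% and 25%). That is true, but it does not answer the lack of stated concealment.

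A reader might also object that 68 is not a multiple of 8. That is immaterial: power at 0.80 SD is 90.2% for 34:34 and 90.1% for 36:32, and varying blocks can leave a similar imbalance.

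**Conclusion.** The point holds as a weakness in allocation concealment that is cheap to remove. Under 1:1 allocation from one list, an observer who knows the block size and past assignments would know 12.8 of 68 assignments on average (18.8%) and guess 66.0% correctly. Of the 1.6 certain assignments per full block, 1.0 is simply the eighth place.

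The figures measure predictability, not bias; no effect on any outcome is estimated. A reader might conclude that allocation will be steered, or that the project manager chooses who comes next. The documents support neither. They show a printed fixed block size, a staff role that acts on each assignment, and no statement that the list or block size is withheld. If a concealed procedure already exists outside the protocol, describing it would settle most of the point. The change should be made, but the gap does not invalidate the design.

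**What to change.** In section 8.1, replace the fixed block size with a statement that assignments use randomly varying block sizes not disclosed to study staff. Sizes such as 6, 8 and 10, or 4, 6 and 8, would serve. The sizes chosen should be recorded only in a randomisation document held by the statistician.

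Because this leaves best-guess accuracy at 66–68%, add two rules. The statistician holds the list, and each assignment is released only after that woman's baseline is complete, with women randomised in order of baseline completion.

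The cost is one line in the list-generating program, a few sentences of protocol text, and a request to the statistician for each woman. The downside is a possible final imbalance of a few women. With even block sizes up to 10 and a stop at exactly 68, the last block ends after an even number of assignments, so the difference is at most 4 (36:32). The present half-filled ninth block has the same limit.

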#### 8.2 Intervention

The baseline assessment will be completed and then the participant will be randomized to computerized cognitive training or attention control group. An immediate post-test will be

completed, which will be 10 weeks after baseline (10 weeks for intervention within 90 days for completing the post-intervention assessment). The first visit will last about 1-hour and all other visits should last about 50 minutes.

At baseline, participants will provide demographic, clinical and treatment information, questionnaire data, blood sample, and complete a neuropsychological assessment administered by a trained and blinded tester. All other assessments will proceed in the same manner; however, demographic and treatment information will not be re-assessed. The medical record of BCS's will be examined for purposes of verifying disease and treatment information, including types and dates of treatments received (surgery, radiation, chemotherapy, tamoxifen and/or aromatase inhibitors). Data will be linked to participants through the use of a unique study-specific identifying number. Only persons on the research team will have access to the data. The neuropsychological tester will remain blinded to the randomization of the participants. All data are collected for research purposes only.

**Cognitive Training:** As tested in our pilot, the Brain HQ program is designed to enhance specific areas of cognitive functioning that will be tested in this study. The goals of the Brain HQ program are to improve visual processing speed, learning and memory and attention. The exercises include time-order judgment, discrimination, spatial-match, forward-span, instruction-following, and narrative-memory tasks. This program systematically reduces the stimulus duration during a series of increasingly difficult information-processing tasks presented via computer. The exercises automatically adjust to user performance to maintain an 85% correct rate. The program will include 4 hours per week over a 10-week period for a total of up to 40 hours. We have support from the original developer and Posit Science. For the purposes of this trial, any participants who do not complete the total of up to 40 hours will not be counted as deviations.

# BrainHQ uses five tasks in the form of computer games designed to improve memory, processing speed, attention, working memory and executive function including:

- Sweep Seeker: The person is asked to clear the rows of blocks presented on the screen, either by moving them into horizontal or vertical blocks that have identical color. The goal is to refine and increase the response of primary visual cortex neurons and to enable the person to increase speed and accuracy of visual processing (executive function) and visual memory.
- 2. Bird Safari: The user is first presented with a target bird. Subsequently, a group of birds is presented in the peripheral vision and then disappears when the trial begins. The user selects the section of the screen where the target bird appeared. The presentation speed adapts with user performance (i.e. better performance = faster presentation). The goal is to improve speed and accuracy of object identification in peripheral vision and improve visual precision important for improving memory.
- 3. Jewel Diver: The person is first presented objects (jewels) on the screen. The objects are then covered with occluders (bubbles) and then identical distracters are presented. The objects move around in screen and when the movement stops, the user chooses the occluders that cover the jewels. The number of jewels adapts to performance (more jewels = better performance). The goal is to improve divided visual attention, sustained visual attention, visual working memory, and visual precision.
- 4. Master Gardener: The person is presented a series of target stimuli and distracters which are presented at one time and then disappear. The locations of the stimuli are marked by icons, and the user choses the icons where the target stimuli were once located. The goal is to increase speed and accuracy as well as the ability to extract information accurately.

5. Road Tour: The person is presented with a target vehicle briefly in both the center of the screen and in one of eight locations in the periphery. Two vehicles are then presented briefly in the center of the screen, one of which is the target vehicle. The user must identify the location of the target vehicle in the periphery as well as identify which was the target vehicle that appeared in the center. The goal of this activity is to improve divided attention and ability to extract information and discard irrelevant information from peripheral vision.

**Attention Control:** Control participants will be asked to complete activities on the computer. The program offers a choice of activities that will consist of crossword puzzles and word jumbles. Attention Control: Computer-based General Cognitive Stimulation Intervention (Computerized Crossword Puzzles): The program offers a pre-determined set of computerized crossword puzzles (www.bestcrosswords.com; http://zone.msn.com/en/crossword; Accessed *09-15-2015*). The site has over 100,000 puzzles and can be accessed easily via the web and are free to users. The computerized crossword puzzles do not provide for progressive challenges of increasing speed, visual field size, number of distractors or degree of difficulty of targeted stimulus differentiation. Training: Participants will be instructed to perform this active attention control intervention 4 hours per week over 10 weeks for a total of up to 40 hours, the same as BrainHQ.

The rationale for this attention control program is (1) it has been routinely and successfully used in other NIH-funded cognitive training trials, (2) it has not shown cognitive benefit in previous research studies, and (3) previous experience by our team and others have shown that it is an appropriate computerized attention control alternative. The delivery format, number of sessions, and setting all parallel the intervention of up to 40 hours over 10 week period. Table 1 describes the difference between the **Brain HQ** intervention and the attention control cognitive training interventions.

Table 1 Comparison of BrainHQ to Attention Control						
Element	Computerized Cognitive Training using BrainHQ	Attention Control Computer-Based General Cognitive	amount required.			
Visual stimuli	Intensive & repetitive with increasing visual stimuli	None	control			
Complexity of stimuli	Progressively increased speed & processing of stimuli with increasing distractions	No Progressive Challenge	the partic in the stu			
Cognitive demand	Tailored; Training adjusted by computer to 85% of individual's threshold	Not tailored; not adjusted or tailored for individual threshold	follow up be condu post in Based or			
Visual attention & memory	Directed attention with each exercise, precision	No directed attention from computerized intervention	the assessme			
Novelty	Individualized feedback and rewards built in to respond to the participant, game features to improve satisfaction	Feedback and rewards not provided, may incur some satisfaction on their own	complete of co interventi attention			

Based on the randomization, the project manager will provide verbal and written instruction for

accessing and using the program and the minimum amount of practice required. BrainHQ and computerized attention control programs will capture the date and time the participants participate in the study.

ntervention: Α assessment will icted immediately tervention (T2). n our pilot study, post-intervention ent and BDNF draw will be d within 90 days ompleting the on (T2) training or control sessions.

edures for

Monitoring Treatment Fidelity: As in our pilot, procedures for monitoring treatment fidelity will

be guided by the Treatment Fidelity Checklist. Both groups have been standardized in dose (length and content) and delivery method (in-home). Intervention dose will be carefully monitored using the computer software built within BrainHQ and Rescue Time software for the active attention control (total time on task). These variables will be examined and used in the analysis. The PI will be responsible for oversight of treatment fidelity The neuropsychological tester will be blinded to group status. The project manager will ensure the participants understand and are utilizing the program. Treatment dose and content will be carefully monitored through the InSight program.

**Qualitative assessment**: individual interviews will be conducted over the phone with members of the intervention group to understand the perceived facilitators and barriers to use of the intervention. All interviews will be conducted after the intervention, voice recorded digitally and labeled with a patient identification number.

Accrual & Retention: Several steps will be taken to ensure high rates of accrual, retention, and representation of minority BCS. These include (1) using culturally appropriate printed study information; (2) contacting potential subjects in person in the clinic, which has been shown to be preferred over unsolicited telephone calls  and to be more effective in recruiting minority subjects; and (3) providing participant incentives of \$20.00 for every assessment completed (\$40.00 for both) to offset subject burden.

